Furthermore, the intestinal microbiomes of infants admitted to NICUs have different patterns compared to infants not admitted to NICUs. This is due to exposure to a different environment in NICUs, and the use of antibiotics and sterile formulas. There is even less data about the establishment of the microbiome in very preterm infants, how that evolves with time, what constitutes a “good” profile and how it correlates with intestinal or systemic pathology. What we know shows that the microbiome in preterm infants demonstrates decreased diversity, altered species proportions and even different behavior of the same species when compared with the term infant (15-17).

2.2 Microbiome and intestinal disease in the neonate.

The microbiome plays an essential role in nutrition, mucosal immunity, and GI epithelial integrity. Current evidence suggests that interactions between the altered microbiome and the intestinal epithelium play an important role in the development of feeding intolerance, allergy, sepsis and necrotizing enterocolitis (NEC) (18-20).

NEC is a multifactorial disease and one of the major pathologies affecting preterm infants. It is associated with significant mortality and morbidity, including long term neurologic disability. Systematic interventions to predict and prevent NEC have generally remained elusive. Feeding breastmilk and colostrum to preterm infants is helpful and use of probiotics has shown good results in a number of studies, though significant concerns remain. Concerns include: the limited safety data for infants born < 1000g and a domestically available probiotic formulation with demonstrated efficacy, safety, and regulatory approval. There remain concerns that the regulatory framework for approval of probiotics does not approach the rigor for drugs (21-22). Systematic reviews of randomized controlled trials concluded that probiotics as a group significantly reduce the incidence of severe NEC (23). The principle and methodology of such generalizations is controversial (24-26). Better tools are needed to aid in the understanding and monitoring of probiotic administration.

The technology available to define the intestinal microbiome has been a sizable obstacle. The vast majority of species cannot be cultured and the genomic technologies have just only very recently reached a level where the ratio of cost and resolution allows for reasonably efficient research use.

2.3 Techniques to study gut microbiota and microbiome.

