3.1 Probiotic administration results in preterm infants

The subject of probiotic administration to preterm infants is important. There are at least 20 meta-analyses and systematic reviews identified with a Pubmed search. This is a large number despite only 24 trials in the latest Cochrane review and a meta-analysis from April 2014 (23). It is also important to note the contradictory statements in that review. It begins by stating: “Based on the available evidence for probiotics efficacy and safety in preterm infants, the number of infants enrolled, the narrow confidence intervals, and the probiotics safety profile, a change in practice is warranted at this stage. More studies to address the optimal preparation, dosing, and duration of therapy are still needed in head to head comparative studies rather than placebo controlled trials.” Immediately followed by: “Although all included trials evaluated probiotics use in preterm infants, the trials were highly variable with regard to enrolment criteria (that is birth weight and gestational age), baseline risk of NEC in the control groups, timing, dose, formulation of probiotic used, and feeding regimens.(23)The validity of our review’s results is potentially compromised as it included trials that utilized different preparations and dosing regimens of the intervention under study; and data on the highest risk population (ELBW infants) could not be retrieved.”

Two sizeable recent studies were published or had outcome data released after the Cochrane review. The recent Probiotics in Preterm babies Study (PiPS) was done in Britain and enrolled 1315 infants of 30 weeks gestational age or less. It used a single bacterial strain – *Bifidobacterium breve*. This study did not find any significant clinical impact of that particular probiotic and the findings do not support the use of *Bifidobacterium breve* for the prevention of NEC (30). Another recent RCT studied *Lactobacillus Reuteri* in 400 VLBW infants of less than 32 weeks gestation and it concluded that there was no effect on NEC

or NEC and mortality though late onset sepsis was significantly reduced (31). The combined size of these 2 studies is large, over 1/3rd of all previous RCTs' population in the 2014 Cochrane review.

3.2 Florababy.

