Florababy is a 5 strain proprietary probiotic blend produced by Renew Life Canada. It contains 4 billion total CFU of 4 *Bifidobacterium* species (*Breve, bifidum, infantis and longum*) together with *Lactobacillus rhamnosus*. The non-medicinal ingredients are maltodextrin and ascorbic acid. Florababy has been used for only a few years in neonates in Canada. A recently published retrospective cohort study compared data from 17 months before and after introduction of Florababy in a level III NICU for all infants less than 32 weeks gestational age at birth (32). It showed a positive impact on NEC stage 2 or more from a baseline of 10% in infants less than 32 weeks, double the current rate in Calgary. The amount of breastmilk feeding in that cohort is not specified. There was no impact on health care associated infections.

3.3 Biology of probiotics and relation with effects – gaps in knowledge.

The above underscores the need for specific product trials in this population as well as the pressing need for markers and biological understanding. A lot of the limited data concerning the fate of probiotics in preterm infants may not be applicable to current NICU care and feeding practices or was generated before latest genomics technology was available (33-43). The percentage of infants and interval of time in which specific probiotic strains are established in the gut, any differences between strains, differences within a population fed fresh breastmilk and correlation with clinical effects including tolerance of enteral feeds and time to reach full feeds are very important aspects. They need to be clarified for contemporary practices, with best methods, in order to assess and optimize the use of probiotics in the neonate. Using meta-analysis to advocate for an intervention when the biological pathways were not clear has been a source of error before in medicine (44).

3.4 Definition of Feeding Intolerance.

Feeding intolerance will be defined as the inability to digest enteral feedings associated with: i) gastric residual volumes of more than 50% of the volume of the previous feed, ii) abdominal distention and/or emesis, iii) disruption of the baby's feeding plan (decrease, delay or discontinuation of enteral feedings).

4. How you are going to do it.

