4.2 Study Population

Premature infants born less than 29 weeks gestation and < 1000g birth weight admitted to the NICU at Foothills Medical Centre in Calgary.

a) Inclusion Criteria: Preterm infants born at less than 29 weeks gestation and < 1000g birth weight.

b) Exclusion Criteria: Infants with major congenital anomalies, hypoxic-ischemic injury and NEC or bowel perforation before 72 hours of life.

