4.4 Variables collected

- a) Demographic variables: Gestational age, birth weight, head circumference at birth, gender, mode of delivery, singleton/multiple and rank, maternal administration of corticosteroids and antibiotics.
- b) Clinical variables: Apgar scores, umbilical cord pH and base excess, first patient blood gas pH and lactate, day of life at start of feeds and at start of study, total days of study drug, antibiotic use during NICU, use of inotropes and vasoactive substances, steroids and medical and/or surgical treatment for PDA, type of feeds during NICU and at discharge.

- c) Outcome variables: mortality; total days of TPN, total days NPO and number of separate NPO events; age, head circumference and weight at discharge home; diagnosis of: feeding intolerance, time taken to reach full enteral feeds (at least 150ml/kg/day), suspected NEC, NEC, cow milk protein allergy, late onset sepsis, BPD, ROP.

4.5 Study protocol.

Infants will be identified within 24 hours of birth and parents will be approached for informed consent.

Once consent is obtained, subjects will be randomly assigned in blocks of 4 to receive either Florababy probiotics orno. Investigators will conduct the randomization using a computer-generated table of random numbers generated at the University of Calgary.

Preparation and Administration of Study Drug

The study probiotic will be started after the first stool sample is obtained and after informed parental consent. Very small amounts of breast milk/colostrum (0.1ml to 0.2ml every 4 hours) are usually given to all premature babies within the first 48 hours of life. Actual feeds of breast and/or human milk (donor milk) are initiated from 72 hours onwards (starting at 10ml/kg/day and increasing slowly thereafter). The study probiotic (at a dose of 0.5g per day) will be started at or after 72 hours of life. It will be administered in 1 ml of sterile water prior to a feed.. No drug will be given to infants in the control group. If the infant is placed NPO, the study drug will be stopped and restarted together with refeeding.

The study probiotic will be given until 34 weeks corrected gestational age.

Sample collection

Nurses will collect the stool samples at 4 time points: prior to, two weeks and four weeks after probiotic administration is commenced, and one week after it is stopped. Stool samples for the control group will be done at a matched feeding and gestational age time points.

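### Section 4.5 restarts Florababy automatically on refeeding, even after NEC or bowel perforation, with no separate decision about the product

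*Protocol*

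**What the plan says.** Section 4.5 (Preparation and Administration of Study Drug) starts Florababy at or after 72 hours of life and sets its scheduled end: "The study probiotic will be given until 34 weeks corrected gestational age". Between those two points there is one rule for interruption: "If the infant is placed NPO, the study drug will be stopped and restarted together with refeeding". Control infants receive nothing.

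Section 3.2 says of the product, "It contains 4 billion total CFU", made up of four Bifidobacterium species and Lactobacillus rhamnosus.

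Section 4.2 limits entry to infants below 29 weeks and below 1000 g. It excludes those with "NEC or bowel perforation before 72 hours of life", along with major anomalies and hypoxic-ischaemic injury. Section 4.4 lists suspected NEC, NEC and late-onset sepsis as outcomes to be recorded and attaches no dosing action to them. The SAP does not deal with dosing.

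**The concern.** The restart is tied to feeding and not to the reason feeding stopped. An infant made NPO for a minor reason and one made NPO for NEC or perforation are handled identically: when milk goes back, so does the live product. Refeeding is a clinical judgement about milk, and no judgement about the product is written down. A clinician who resumes feeds after NEC but withholds Florababy would be departing from the protocol.

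A lesser gap concerns an infant who is still being fed and from whom a Florababy organism is isolated at a sterile site. Such an infant is not NPO, so no written rule stops the product before 34 weeks.

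The protocol itself gives the reason for care. Section 2.2 names as a concern "the limited safety data for infants born < 1000g", and section 3.1 quotes a systematic review reporting that "data on the highest risk population (ELBW infants) could not be retrieved". What is at stake is a re-exposure decision in very small infants that is made by default when it could be made deliberately. The validity of the primary comparison is not in question.

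**Working it through.** **1. Which written rules can stop the product.**
- NPO status: a hold, lifted by refeeding.
- Reaching 34 weeks: the scheduled end.
- The NEC/perforation exclusion cannot act on treatment, because its window closes at 72 hours and dosing starts no earlier than that.

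Nothing else in the protocol or SAP holds or ends dosing. An infant with NEC after 72 hours is made NPO, held, refed and restarted. A fed infant with a sterile-site isolate meets neither stopping condition until 34 weeks.

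**2. How many infants.** Section 3.2 gives a baseline of 10% for NEC stage 2 or more below 32 weeks in the published Florababy cohort and describes this as twice Calgary's rate, so Calgary is about 10% / 2 = 5%. Among 30 treated infants:
- at 2.5%: 30 × 0.025 = 0.75
- at 5%: 30 × 0.05 = 1.5
- at 10%: 30 × 0.10 = 3

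These count all NEC. The rule affects only infants who survive and are refed before 34 weeks, which lowers the count. The rate below 1000 g, the rate on Florababy and the perforation rate are not given, so the true number could be higher or lower. No rate is given for sterile-site isolates, so none is offered.

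**3. How long the rule can operate.** Dosing window = 238 days (34 weeks) − gestational age at birth − 3 days.
- Birth at 28w6d (202 days): 238 − 202 − 3 = 33 days
- Birth at 24w0d (168 days, an assumed lower end): 238 − 168 − 3 = 67 days

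If dosing starts at 72 hours, the week-4 sample falls 28 days into this window. Between 33 − 28 = 5 and 67 − 28 = 39 days of dosing therefore lie after the primary sample.

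**4. The plan's own power (section 4.3).** Inputs: 30 per arm, two-sided Wilcoxon-Mann-Whitney test, alpha 0.05, effect size 0.7, logistic parent. Under the asymptotic relative efficiency method:
- ARE = π²/9 = 1.097
- effective n per arm = 30 × 1.097 = 32.9
- degrees of freedom = 2 × 32.9 − 2 = 63.8
- noncentrality = 0.7 × √(32.9/2) = 2.84
- power = 0.798, which reproduces the stated 0.8

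**5. What lost dosing could cost.** Suppose every treated infant with NEC lost the whole week-4 effect. The effect becomes 0.7 × (1 − rate), with the spread held unchanged:

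| NEC rate | Effect size | Power |
|---|---|---|
| 0 | 0.700 | 0.798 |
| 2.5% | 0.683 | 0.778 |
| 5% | 0.665 | 0.757 |
| 10% | 0.630 | 0.711 |

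For NEC this overstates the added loss. These infants are already off product while NPO, some NEC falls after the week-4 sample, and restart stays possible. It is not an upper bound for the whole change, because perforations and isolates are left out for want of a rate.

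**The case against.** The strongest reply is that the existing rule is coherent and already covers the acute illness. Product is stopped at NPO and follows feeding throughout: it begins around the time feeds begin, is given before a feed, pauses with feeds and returns with them. Clinicians choose when to refeed, and nothing forbids them from stopping the product. Many infants with sepsis or NEC would be NPO in any case. The documents also hold reassuring evidence. Section 2.2 reports a review conclusion that "probiotics as a group significantly reduce the incidence of severe NEC". Section 3.1 describes a 400-infant trial of another product in which "late onset sepsis was significantly reduced" and a 1315-infant trial with no significant clinical impact. Section 3.2 reports less NEC with Florababy below 32 weeks and no change in hospital-acquired infection.

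Much of this stands. It reduces the sterile-site case to a secondary clause, since that case is an argument from silence and good practice would probably handle it. It does not remove the restart after NEC or perforation, which is a written instruction. None of the reassuring evidence is specific to infants below 1000 g or to restarting after NEC.

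Three stronger readings are tempting and are not supported:
- **The product is harmful in these cases.** No figure in the documents shows this, and the general evidence points the other way.
- **The plan contradicts itself by excluding early NEC but allowing restart after later NEC.** An entry criterion decides who is enrolled and a hold rule manages infants already randomised. The two need not match, and a criterion ending at 72 hours fits dosing that starts then.
- **The trial has no safety oversight.** Ethics-board reporting procedures may exist outside these documents. The point concerns the dosing rule alone.

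**Conclusion.** The point holds as a low-priority safety improvement. That the restart is unconditional is certain from the text. Its consequence is not measured. About 1.5 of 30 treated infants would have NEC (0.75 to 3 at 2.5% to 10%), resting on a rate for infants below 32 weeks carried over to infants below 1000 g. Only those who survive and are refed before 34 weeks would be re-exposed, and perforations would add an unknown number. The missing stop for a sterile-site isolate is secondary and carries no estimate. Neither gap biases the primary comparison. The case for change is that a re-exposure decision in a population with limited safety data should be deliberate, and that making it so costs little.

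**What to change.** Add to section 4.5:

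> After NEC or bowel perforation, study product restarts only on a documented decision about the product by the clinical team and investigator, not on refeeding alone. Product is stopped if a species contained in Florababy is isolated from a sterile site. Otherwise the existing NPO rule applies. Infants whose product is stopped early stay in their randomised arm, and their stool samples are taken at the originally scheduled times, with the final sample one week after 34 weeks corrected age.

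The last sentence is needed because section 4.5 times the fourth sample from the end of dosing. An early stop would otherwise leave that sample, and its matched control, undefined. For such infants the final sample will reflect a longer period off product than in others. The SAP should carry the same sentence, since it does not currently say how these infants are analysed. The tests themselves do not change.

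Cost: one paragraph, an ethics-board amendment and about one or two documented decisions at 5% NEC, plus any perforations or isolates. Controls receive nothing, so no unblinding is involved. The downside is some lost dosing days and a slight dilution of the week-4 contrast: power about 0.76 if 5% of treated infants lost the whole effect, counting NEC only.

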Do probiotics modulate the intestinal microbiome in extremely premature infants?

Principle Investigator: [name]

REB16-0542

October 11, 2017

Project Title: Do probiotics modulate the intestinal microbiome in extremely premature infants?

Project Type: Primary – Research
Secondary – Clinical care

Principal Applicant (PA): [name] (Concept, literature review, study design, drafting application)
Co-Principal Applicant: [name] (Concept, study design and statistics, drafting application)

Collaborators: [name] (Microbiome Research Scientist)
[name] (ACHRI - Sample analysis)
[name] (MSc student in Microbiology)
[name] (Infection prevention and control)
[name] (Epidemiology and data analysis)
[name] (ACH/FMC pharmacists: product management)

Project Summary:

The gut microbiome plays a significant role in balancing the inflammatory system in the immature gut. A breakdown in this balance with altered colonization of the microbiota in very low birth weight (VLBW) preterm infants is associated with increased feeding intolerance, NEC and sepsis. Probiotics are proposed to normalize microbial populations and decrease intestinal disease in preterm infants. There is limited data linking clinical outcomes with the biology of probiotics. We aim to study the colonization of the GI tract with probiotic species contained in a specific probiotic blend – Florababy – in VLBW preterm infants.

Stool microbiome will be analyzed at 4 time points in 2 groups (one given Florababy and the other no) of infants less than 1000g birth weight and < 29 weeks gestation. A comparison of stool microbiome analysis and the incidence of feeding intolerance and time to reach full feeds in the two groups will be made.

1. What you want to do.

Research question

Does Florababy change the gut colonization pattern in a measurable way in a population of very premature neonates?

Hypothesis:

Florababy probiotics can multiply in the gut and change the colonization pattern of the premature intestinal tract in a measurable way.

Primary outcome: difference in stool microbiome after 4 weeks of Florababy or compared to infants who didn't receive Florababy.

Secondary outcomes: i) difference in stool microbiome 1week after the study drug administration is stopped.

ii) incidence of feeding intolerance and time to reach full feeds.

3. Why this is important.

At a glance:

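### The control-arm stool clock is undefined and rests partly on feeding, so equal age at the primary 4-week stool is not assured

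*Protocol*

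**What the plan says.** **Treated arm.** Protocol section 4.5 (Sample collection) takes stools "prior to, two weeks and four weeks after probiotic administration is commenced, and one week after it is stopped". Under Preparation and Administration of Study Drug, the product follows the first stool sample and "will be started at or after 72 hours of life", with no upper limit. The end is fixed by age: "The study probiotic will be given until 34 weeks corrected gestational age".

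**Control arm.** Controls receive no product, so they have no first dose to count from. The only timing rule is: "Stool samples for the control group will be done at a matched feeding and gestational age time points".

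**Allocation and matching.** Section 4.5 states: "Once consent is obtained, subjects will be randomly assigned in blocks of 4". Section 4.3 says the groups will be matched on several baseline factors, including gestational age within one week, but pairs no individual infants.

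**Outcomes.** Section 1 makes the between-group stool difference after 4 weeks the primary outcome. It lists "incidence of feeding intolerance and time to reach full feeds" among the secondary outcomes.

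**Data and analysis.** Section 4.4 collects day of life at the start of feeds and at the start of study, but not age at each stool. Neither section 4.6 (Bioinformatic analysis) nor the SAP has a term for age at sampling in the Shannon, PERMANOVA or DESeq2 analyses.

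**The concern.** The two arms are sampled on different clocks. One runs in days from a defined event. The other depends on a match that the protocol does not define, and one of its two criteria is feeding. Randomisation follows consent, which is sought once infants are identified within 24 hours of birth, while real feeds begin from 72 hours. Feeding progress is therefore usually post-randomisation, and the trial itself treats it as something the product may change.

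Section 2.1 names gestational age and feeding patterns among the factors that alter neonatal gut flora. If control stools were taken at a systematically different age, some of the 4-week difference could reflect age rather than the product. If controls were instead held to the same feeding stage, any effect that runs through feeding would be partly removed. With no age at stool among the listed variables and no such term in the models, the planned analyses could neither detect nor correct this. A mistimed stool cannot be collected again.

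**Working it through.** **Step 1. Is the control time point determined by the text?** Two terms are open.

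| Term | Possible meanings | Consequence |
|---|---|---|
| Feeding | Days since first feed, or feed type | Days since first feed can hardly be affected, since the product starts at about the time feeds do; neither meaning is the secondary outcome |
| Feeding | Stage or volume reached | Post-randomisation; closely tied to time to full feeds |
| Gestational age | Corrected age at sampling | Limits the age gap if it takes priority |
| Gestational age | Age at birth | Does not fix the age at which the stool is taken |

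The protocol selects none of these. It gives no tolerance and no order of priority. Allocation in blocks of 4 supplies no partner, so a control enrolled before any treated infant has nobody to match.

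**Step 2. When do the criteria conflict?** Only if feeding means stage reached and the product changes feeding. The arms then reach a given stage at different ages on average. Holding stage fixed moves age; holding age fixed moves stage. Interruptions show the asymmetry under this reading: the treated clock runs on from the first dose while an infant is NPO, whereas a control who is NPO could fall behind on feeding stage and be sampled later.

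**Step 3. Which samples are exposed?** Mainly those at 2 and 4 weeks. The fourth follows a stop at a fixed corrected age, which controls also reach.

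**Step 4. Reproduce the planned power.** Inputs from section 4.3: n = 30 per arm, two-sided alpha 0.05, Wilcoxon-Mann-Whitney test, effect size d = 0.7, logistic distribution. The asymptotic relative efficiency (ARE) is π²/9 = 1.0966.

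- df = 2n × ARE − 2 = 2 × 30 × 1.0966 − 2 = 63.8
- Non-centrality = d × √(n × ARE / 2) = 0.7 × √16.449 = 2.84
- Power from the non-central t distribution = 0.7985; by simulation (20,000 trials) 0.784

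The stated 0.80 is reproduced. This point does not affect the sample size.

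**Step 5. Sensitivity to an age-related shift.** The documents give neither a rate of change of the microbiome with age nor a difference in feeding between arms. Both are assumed here. Shift = drift per week × days of gap / 7, entered as d in the step 4 formula with no true effect.

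| Mean age gap | Shift at 0.1 SD/week | Rejection | Shift at 0.3 SD/week | Rejection |
|---|---|---|---|---|
| 0 days | 0 | 5% | 0 | 5% |
| 3 days | 0.04 SD | 5.3% | 0.13 SD | 8.1% |
| 7 days | 0.10 SD | about 7% | 0.30 SD | 22.4% |

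A shift of 0.2 SD gives 12.6%. Simulation gives 6.4%, 11.8% and 21.8% for shifts of 0.1, 0.2 and 0.3 SD.

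**Step 6. With a true effect.** If the true effect is 0.7 SD, a bias of −0.2 SD leaves an apparent 0.5 SD and power of 51%; +0.2 SD gives 0.9 SD and 95%. The direction cannot be told from the documents.

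These figures apply to a single continuous measure compared by the Wilcoxon-Mann-Whitney test, not to PERMANOVA or DESeq2.

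**The case against.** The control sentence names gestational age beside feeding. If that means corrected age at sampling and it governs, any age gap is limited by the rule itself. Matching on feeding may mean no more than days since feeds began or type of feed. Section 4.4 collects the start of feeds and the type of feeds, which fits either reading, and neither is the secondary outcome. Section 2.1 also gives a reason to align the arms on feeding, since it affects the flora. It reports no weekly drift for this population.

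The rejection rates are open to challenge too. They assume no true effect, yet the mechanism needs a product that changes feeding. A product that shifts feeding by about a week and leaves the microbiome untouched is not an obvious scenario, and both drift and gap are assumed.

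Most of this stands. It rules out two inferences a reader might draw: that controls are timed by feeding alone, so that an age difference is built in; and that a control can never match on both feeding and age. The first overlooks half of the sentence. The second turns a difference in averages into an impossibility for individual infants.

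The objection does not remove the point, because the protocol adopts none of the benign readings. No blinding is described and controls receive nothing, so staff who know the allocation could be the ones to interpret an open rule.

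**Conclusion.** The concern holds in a limited form. The control sampling rule has no partner, window or priority rule, and one of its two criteria is usually post-randomisation and closely tied to a secondary outcome. If it refers to feeding stage and the product changes feeding, equal age at the primary 4-week stool is not assured, or part of the effect is conditioned away.

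This is more than missing detail, because timing for the primary contrast may depend on something treatment affects. It is not a demonstrated bias, and its size cannot be derived. The illustrative range is a rise from 5% to about 7% to 22% for an assumed shift of 0.1 to 0.3 SD, and no rise if there is no age gap. A reader should not infer that the trial has an inflated false-positive rate of any particular size.

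**What to change.** Put both arms on one clock.

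- Give each control a notional start day, set by the conditions that section 4.5 already applies to the first dose in the treated arm.
- Collect control stools before that day, at 14 and 28 days after it, and one week after the corrected age at which the protocol ends dosing, whatever the later feeding progress.
- Delete the feeding criterion from the control sentence.
- Record actual age at every stool in both arms.
- Add to the SAP a sensitivity analysis with age at sampling as a covariate.

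The start of feeds may itself follow randomisation. It is fixed at about the time dosing begins, however, so the product can hardly influence it, unlike later feeding progress.

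The cost is a start-day field for controls, an age-at-stool field and revised wording. The number of stools and infants is unchanged. The arms may then differ in feeding stage at a given stool; that is part of the treatment effect and should not be matched away. The change has to be in place before stools are collected.
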